13.2 Serious Adverse Events (SAE)

13.2.1 Definitions

Serious Adverse Event: Any untoward medical occurrence that at any dose:

- Results in death,
- Is life-threatening,
- Requires inpatient hospitalisation or prolongation of existing hospitalisation,
- Results in persistent or significant disability or incapacity,
- Is a congenital anomaly or birth defect
- Is an important medical event

Death: The death of a patient enrolled in a clinical study is per se not an event, but an outcome. Any AE resulting in a fatal outcome must be fully documented and reported, including situation for which the death occurred after treatment end, and regardless of the causality relationship between the death and the IMP. The cause of the death is usually the AE. If the cause cannot be determined, the case will be considered an unexplained death.

Life-threatening: Any AE that places the patient, in the view of the initial reporter (investigator), at immediate risk of death from the AE as it occurred, i.e. it does not include an AE that, had it occurred in a more severe form, might have caused death.

Disability: A substantial disruption of a person's ability to conduct normal life functions.

Important medical event: An important medical event that may not result in death, be life-threatening, or require hospitalisation may be considered as a SAE when, based upon appropriate medical judgement, it may jeopardise the patient and may require medical or surgical intervention to prevent one of the outcomes listed in the definition. The concept includes AEs which suggest a significant hazard, contraindication or precaution for use, occurrence of malignancy or development of drug dependency or drug abuse.

13.2.2 Other Events to be Treated as Serious Adverse Events

Exposure to drug during pregnancy: In principle, pregnancy and the lactation period are exclusion criteria for clinical studies involving investigational drugs, which are not directly related to the respective conditions. In the event of a pregnancy occurring during the course of this particular study, the patient should be withdrawn from study, but closely followed-up during the entire course of the pregnancy and postpartum period.

Investigational Product Complaints: Pharmaceutical technical complaints associated with the investigational product must be reported immediately. The same reporting timelines as for SAEs apply.

13.2.3 Reporting of Serious Adverse Events

If any SAE occurs, the investigator will take appropriate action immediately and will strive to identify the causes of the events.

SAEs will be notified by the Investigator to Stragen Services, acting on behalf of the Sponsor, as soon as possible, i.e. within 24 hours from first knowledge by e-mail or fax to:

E-mail: [contact]
[contact]
[contact]

Stragen Services acknowledges the receipt of the SAE information by email to the investigational site within one working day. In the absence of email acknowledging the receipt or in case of issue in sending the fax or email, the investigator shall contact Stragen Services by any means for ensuring the receipt of SAE information at the earliest opportunity.

Any follow-up information will be reported to Stragen Services as soon as it becomes known, with the same process and timelines as described here above for initial reports. Photocopies of results, consultant report(s), a summary of the outcome of the reaction and the Investigator's opinion of IMP relationship to the SAE will accompany the SAE form if and when available.

The Sponsor will also perform an evaluation of the seriousness, causality and expectedness of all SAEs. All SAEs judged by either the Investigator or the Sponsor as having a reasonable suspected causal relationship to an IMP (i.e. probably or possibly related) will qualify as serious

adverse reactions. If the Sponsor disagrees with the Investigator's causality assessment, both the opinion of the Investigator and the Sponsor are provided with the report.

All reported SAEs will be included in the INOTREM SA pharmacovigilance database.

Suspected unexpected serious adverse reactions (SUSARs) are AEs which have a reasonable possibility to be related to an IMP and are both unexpected (i.e. the nature or severity is not expected from the information provided in the investigator's Brochure) and serious. SUSARs are subject to immediate (ANSM)/within 7 days expedited reporting to the Competent Authorities and Ethics Committees.

SUSARs will be notified to the Competent Authorities and to the relevant ECs by Stragen Services immediately (ANSM)/within 7 days (other Competent Authorities) (for fatal and life-threatening SUSARs) or 15 days (all other SUSARs), with follow-up information in the following 8 days. The decision on the reportability will be made by the sponsor.

Annual safety reporting to the Competent Authorities and the Ethics Committees will be in agreement with ICH guideline E2F "Note for guidance on development safety update reports (DSUR)".

In addition, any other safety issue, such as any new fact including information which may alter the current benefit-risk assessment of the IMP or the concerned clinical trial, which may lead to changes in the use of the IMP, in the conduct of the clinical trial, or of its related documents including the study protocol, or which may lead to suspend or terminate this clinical trial or similar researches, which may alter the current benefit-risk assessment of the IMP will be reported by the Sponsor (or delegate) immediately (France) or on an expedited basis to Health Authorities, Ethics Committees and the Investigators.

The specific reporting modalities implemented by French Decree number 2016-1537 dated 16 November 2016 for clinical trials involving healthy/patient volunteers are applicable for all parts of this study.

13.3 Recording of Adverse Events and Follow-Up

All (serious and non-serious) adverse events detected by the Investigator or delegates, or spontaneously notified by the patient at each visit/examination must be reported on the respective section of the eCRF.

The following information should be reported for each adverse event, whether or not it can be attributed to trial drug:

- description of adverse event
- date of onset/date of disappearance
- characteristics of the event (seriousness, intensity)
- actions taken (treatment required or dose adjustments must be reported in the CRF)
- outcome
- relationship with trial drug (causality assessment) and/or study participation

All adverse events must be documented and followed up until the event is either resolved or a satisfactory explanation is found, or the investigator considers it medically justifiable to terminate the follow-up.

Any AEs that are unresolved at the patient's last AE assessment in the study (i.e. at the end of study visit) are to be followed up by the Investigator for as long as medically indicated. INOTREM SA retains the right to request additional information for any patient with ongoing AE(s)/SAE(s) at the end of the study, if judged necessary.

Findings and values related to physical examinations and measurements of ECG, vital signs, (temperature, blood pressure, and heart rate) and laboratory parameters will be defined as AEs if they are considered clinically relevant deteriorations compared with screening values, as judged by the investigator.

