11.2 Screening / Pre-treatment Period

The purpose of the screening/ pre-treatment phase is to confirm patient eligibility for enrolment in the study based on the inclusion and exclusion criteria and to obtain written informed consent.

Patients who meet all of the inclusion criteria and none of the exclusion criteria and have provided informed consent can be enrolled in the study.

Note: Before confirming the eligibility of a patient, adequate fluid therapy as recommended in the current guidance of the Surviving Sepsis Campaign (see appendix 1) should be applied.

During the Screening/Pre-treatment period and after obtaining informed consent, the following assessments will be performed:

- Medical history and demographics
- Date of current hospital admission, ICU admission and initiation of invasive mechanical ventilation
- Time and details of fluid and vasopressor therapy
- Previous therapies (within 24 hours prior to screening)
- APACHE II score
- Serum pregnancy test in all female patients
- Physical examination
- Weight and height
- Vital signs
- ECG
- SOFA score
- Blood sample for arterial blood gases (ABG). P/F will be calculated, using equivalence tables for non-ventilated patients
- Clinical laboratory (see Table 2)
- Phone call with the CCC to approve patient inclusion in the study
- Randomisation

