12.9 Sepsis Related Clinical Events

Clinical events related to severe sepsis or sepsis complications will be collected. The following events will be considered clinical events related to severe sepsis or sepsis complications:

- Death related to severe sepsis, that is, related to severe sepsis or a sequela of sepsis based on the interpretation of the investigator.
- Cardiovascular events: the need for vasoactive drugs, hypotension.
- Respiratory events: decreased $\text{PaO}_2/\text{FiO}_2$, mechanical ventilation, hypoxia, acute respiratory distress syndrome, acute lung injury, or respiratory failure.
- Hepatic events: hepatic injury or liver dysfunction that leads to an increase from baseline in the serum level of bilirubin or other LFTs.
- Renal events: renal failure, renal insufficiency, or renal injury that leads to an increase from baseline in serum creatinine.
- Hematologic/coagulation events: coagulopathy, disseminated intravascular coagulation, thrombocytopenia, or thrombocytosis.
- Systemic inflammatory response syndrome related criteria: tachypnea, hypopnea, leukocytosis, leukopenia, hypothermia, tachycardia, or bradycardia.

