13 ADVERSE EVENTS

13.1 Adverse Events

Safety will be determined by an evaluation of physical examination, vital signs, ECG parameters, laboratory tests and by the occurrence of Adverse Events (AEs).

Adverse event (AE): Any untoward medical occurrence in a patient or clinical study subject administered a medicinal product and which does not necessarily have a causal relationship with this treatment. Events occurring prior to the first administration are part of baseline information.

An adverse event (AE) can therefore be any unfavourable and unintended sign (including an abnormal laboratory finding), symptom, or disease temporally associated with the use of an investigational medicinal product, whether or not considered related to the investigational medicinal product.

Adverse reaction (AR): All untoward and unintended responses to an IMP related to any dose administered.

All adverse events judged by either the reporting investigator or sponsor as having a reasonable suspected causal relationship to an investigational medicinal product are qualified as adverse reactions. The expression reasonable causal relationship means that there is evidence or argument to suggest a causal relationship.

Multiple signs or symptoms: If an AE consists of several signs or symptoms that can be represented by one single syndrome or diagnosis, the syndrome or diagnosis will be recorded in the CRF as the AE instead of the individual signs or symptoms.

Worsening: Signs, symptoms, syndromes or diagnoses present before the first administration of the IMP will be considered as AEs if they worsen after the start of the IMP.

AE collection: The condition of the patients will be monitored throughout the study from the time of signed Informed Consent up to the end of the study (day 28). The investigator will collect the AEs reported spontaneously, observed, or elicited in response to a non-leading question (for example, "How have you been feeling since we last asked you?"). The investigator will record all AEs in the source records and the eCRF.

Study specific definition:

Clinical events related to severe sepsis or sepsis complications are recorded on the appropriate eCRFs (see section 12.9). When serious, these clinical events are exempt from serious adverse event reporting, unless the investigator deems the event to be related to the administration of the study drug. The following events will be considered clinical events related to severe sepsis or sepsis complications:

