15.1 Statistical Methods

15.1.1 General Considerations

The analysis will be computed with SAS Version 9.4 (Copyright© 2013 by SAS Institute Inc., Cary, NC, USA).

Unless otherwise specified, baseline is defined as the last planned assessment prior to first dosing and no subgroup analysis is currently planned.

Missing safety, pharmacodynamic, pharmacokinetic and clinical data will not be replaced and will be treated as missing from summary and statistical analyses.

Unless otherwise specified, all treatment comparisons will be two-sided and significance will be assessed at the 5% level.

All safety, pharmacokinetic, pharmacodynamic and clinical data will be summarised by treatment group (Placebo, Dose level 1, Dose level 2 and Dose level 3), and visit, as appropriate.

Qualitative variables will be presented using the number of patients, the number of missing values, the frequency and the percentage per modality.

Quantitative variables will be reported using the number of patients, the number of missing values, the mean, the standard deviation, the median, the first and the third quartiles, the minimum and the maximum.

Between groups comparisons are calculated using an independent t-test or ANOVA-test for quantitative variables with a parametric distribution, or Mann-Whitney test or Kruskal Wallis-test for variables with a non-parametric distribution.

Data is tested for normality using Kolmogorov-Smirnov-test.

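### Section 13.3 judges ECG, vital-sign and laboratory adverse events against screening, while 13.1, 15.1.1 and 15.1.5 use the pre-dose state, so some post-dose worsening can go unrecorded as an AE

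*Combined protocol and SAP*

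**What the plan says.** Section 13.3 of the protocol covers findings from physical examination, ECG, vital signs and laboratory tests. They "will be defined as AEs if they are considered clinically relevant deteriorations compared with screening values, as judged by the investigator".

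Other sections use a different reference point:

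- Section 13.1: "Events occurring prior to the first administration are part of baseline information". Signs or diagnoses already present before the first dose "will be considered as AEs if they worsen after the start of the IMP".
- Section 15.1.1: unless otherwise specified, "baseline is defined as the last planned assessment prior to first dosing".
- Section 15.1.5: a treatment-emergent event either starts after the first dose or was present before it and then became more severe. Laboratory, vital-sign and ECG changes are described from baseline.
- Section 12.9 uses baseline for two kinds of sepsis-related event: hepatic ("liver dysfunction that leads to an increase from baseline in the serum level of bilirubin or other LFTs") and renal ("renal injury that leads to an increase from baseline in serum creatinine"). It does not define the term there, so its pre-dose meaning has to be borrowed from 15.1.1.

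Sections 11.2 and 11.3.1, with Table 1 and its footnote 2, schedule vital signs, ECG, arterial blood gases and clinical laboratory tests at screening and again before treatment starts on Day 0. Section 11.2 lists a physical examination at screening; 11.3.1 does not repeat it. Table 2 takes laboratory values from the first routine sample of the day. No section says which reference governs.

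**The concern.** The same finding can be an AE under one section and not under another. Safety and tolerability is the primary endpoint (15.1.3), and finding-based AEs enter its tables through whichever rule the site follows.

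The case that matters is a patient whose value improves between screening and dosing and then falls back after the infusion starts. Compared with the pre-dose reading this is a deterioration on treatment. Compared with screening it is not a deterioration, and 13.3 gives no reason to record it. That patient would show a worsening in the change-from-baseline tables and have no matching entry in the AE tables.

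**Working it through.** The plan gives no figure to reproduce. The check is to set the rules side by side and list every case in which they differ.

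**Notation.** For one measurement, with higher meaning worse: S = screening value, B = Day 0 pre-dose value, P = post-dose value. For the comparison, any rise counts as clinically relevant.

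- Section 13.3: AE if P > S.
- Sections 13.1 and 15.1.1: AE if P > B.

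**The six strict orderings.**

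| Ordering | 13.3 (P > S) | 13.1 (P > B) | Agree? |
|---|---|---|---|
| S < B < P | AE | AE | yes |
| B < S < P | AE | AE | yes |
| P < S < B | no | no | yes |
| P < B < S | no | no | yes |
| B < P < S | no | AE | **no** |
| S < P < B | AE | no | **no** |

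The rules differ in 2 of 6, once in each direction. Allowing ties there are 13 orderings and the rules differ in 4. The two added are B < S = P (13.1 only) and S < B = P (13.3 only). These are logical cases, not frequencies.

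**Following each disagreement into the AE tables.**

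1. *B < P ≤ S: better before dosing, worse after it, not beyond screening.* Read literally, 13.3 creates no AE. Section 13.1 would. If the site follows 13.3, the event is absent from the AE data and nothing later in the AE tables restores it.
2. *S < P ≤ B: worse before dosing, no worse after it.* Section 13.3 makes this an AE. But AEs are recorded from informed consent (13.1, 13.4), and 11.3.1 schedules an AE check together with the measurements before the first dose. The worsening is therefore visible on Day 0. Section 13.3 requires the onset date, and 15.1.5 admits a pre-dose event only if it later increased in severity. Correctly dated, the event stays out of the treatment-emergent tables. It enters only if its onset is wrongly dated to a post-dose reading.

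**Scale of one case.** Section 15.2 plans 12 patients per group. One patient misclassified in either direction changes that group's incidence of the event by 1/12 = 8.3 percentage points.

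**The case against.** The strongest answer is that 13.3 does not exclude anything. It says when a finding becomes an AE, not that nothing else can be one. Section 13.1 independently defines an AE as any unfavourable sign, laboratory abnormalities included, and counts post-dose worsening of what was already there. An investigator who applies 13.1 will report the missed case. This stands in part: it turns the problem from an exclusion into an ambiguity, and recording then varies with the section a site follows. Section 13.3 is the specific rule for these findings, so following it literally is a natural reading.

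Several limits stand in full. The measurements are not lost, because 15.1.5 lists them by patient and visit, identifies abnormal values and describes changes from baseline. Clinical relevance is the investigator's judgement, not a threshold. Some screening and Day 0 laboratory values may be the same sample. For physical examination, screening is the last scheduled pre-dose assessment, so there is no conflict.

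A reader might infer that the screening reference shrinks the drug-placebo difference. The documents do not support this. They give no data on change between screening and dosing, and the direction turns on what is assumed. As an illustration only, let the post-dose change be normal with SD 1 and mean 0 on placebo or 0.5 on drug, and let an event be a rise of at least 1. Judged from pre-dose, the rates are 15.9% and 30.9%, a difference of 15.0 points. Now add a screening-to-pre-dose change with SD 0.5, so that the total SD is √(1 + 0.25) = 1.118. If values improve by 0.5 on average before dosing, the rates judged from screening are 9.0% and 18.6%, a difference of 9.6 points. If they worsen by 0.5, the rates are 32.7% and 50.0%, a difference of 17.3 points. Neither case is documented, so no percentage of missed events should be attached to this trial.

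A reader might also take the 24-hour limit as the gap between the two readings. It runs from the start of vasopressors to the start of study drug (8.1). Fluid therapy should be given before eligibility is confirmed (11.2), so initial resuscitation may largely precede screening.

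**Conclusion.** The inconsistency is real and nothing in the document reconciles it. Followed literally, 13.3 can leave a post-dose deterioration out of the AE tables when the value stays within its screening level, while 13.1 would count it. That makes recording of part of the primary endpoint site-dependent.

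The stronger reading, that pre-dose worsening is routinely counted as treatment-emergent, does not hold: it requires a dating error. The size and direction of any effect on the drug-placebo difference cannot be derived from the documents. What can be said is that each affected patient is 8.3 points of one group's incidence at the planned 12 per group.

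The conclusion assumes that baseline in 12.9 and 15.1.5 carries the 15.1.1 meaning and that the screening and Day 0 readings are distinct, which the schedule supports most clearly for ECG and vital signs. The change is worth making because it is cheap and concerns the primary endpoint.

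**What to change.** In 13.3, replace the reference to screening by *the last assessment before first dosing (screening only where no Day 0 pre-dose value exists, for example physical examination)*. This brings it into line with 13.1 and 15.1.1.

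Rewording does not alter AEs already recorded, and the protocol's history of changes, which refers to an original analysis and to retrospective collection, suggests that recording may be complete. For existing data, add one programmed listing with two parts:

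- clinically relevant post-dose worsening from the Day 0 pre-dose value with no AE recorded;
- finding-based treatment-emergent AEs whose Day 0 pre-dose value was already at the same level.

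The cost is one phrase, one listing and some medical review of what it shows. No new measurements are needed, because the Day 0 pre-dose values are already scheduled. Sample size and error rates do not change.

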13.4 Period of Observation

Adverse events (serious and non-serious) will be recorded and reported to the sponsor from the time of written informed consent to the end of study (Day 28).

Relevant changes to patient's status will be recorded until day 90.

14 QUALITY ASSURANCE AND QUALITY CONTROL

Monitoring and auditing procedures developed or endorsed by the Sponsor will be followed in accordance with GCP guidelines. Direct access to the on-site study documentation and medical records must be ensured.

14.1 Monitoring and Source Data Verification

All aspects of the study will be carefully monitored by the sponsor, or designee, for compliance with applicable government regulations with respect to Good Clinical Practice (GCP) and current standard operating procedures.

The monitoring of this study will be performed by the Sponsor's Monitor(s) or a designee in accordance with the principles of GCP as laid out in the International Conference on Harmonisation (ICH) "Good Clinical Practice: Consolidated Guideline".

The clinical monitor, as a representative of the Sponsor, has an obligation to follow the study closely. In doing so, the monitor will visit the Investigator and site periodically as well as maintain frequent telephone and letter contact. The monitor will maintain current personal knowledge of the study through observation, review of study records and source documentation, and discussion of the conduct of the study with the Investigator and staff. Further details will be described in the SOM.

